The overall goal of this project is to provide feasibility data for a novel method of defining patient-specific functional anatomic targets for GPi DBS placement.

Aim 1. To evaluate the feasibility of a novel, clinically applicable 3 Tesla (3T) MRI protocol for functional segmentation of the GPi based on connectivity measures derived from MRI diffusion-weighted imaging.

- a) Assess the ability of spatially localizing the motor functional representation within the GPi in individual subjects with a clinically feasible imaging protocol using widely available 3T MRI.

Aim 2. To determine the variation in degree of overlap between the traditional atlas-based target point and the derived MRI functional segments on pre-operative imaging

- a) To better understand the relationship of the traditional target point and the functional segments, we will compare the degree of overlap. We hypothesize that the traditional target point will show variation between subjects in the degree of overlap with each functional segment suggesting inadequacy of structural targeting methods that are based on generalizations rather than patient-specific functional targets

Aim 3. To compile preliminary evidence for the role of a patient-specific, functional-based targeting protocol to replace potentially inaccurate atlas-based methods in treating Parkinson's disease that can be implemented on commonly available 3T MRI scanners

- a) Based on the stimulation parameters used to achieve a satisfactory treatment response, a model of the volume of activated tissue will be generated. The degree of overlap between this volume of tissue will be assessed on both the pre-operative functional target and the original atlas-based target. We hypothesize that the volume of activated tissue will closely overlap with the functional segment most connected to the motor and pre-motor cortex.
- b) Current data will be the basis for pursuing additional funding for implementing the 3T protocol in a larger patient cohort to further explore the potential role in treatment targeting
- c) Eventual long-term goal will be acquisition of external funding for a clinical trial using the targeting sequence prospectively to assess the overall goal of this investigation: improving success rate and decreasing complication rate by addition of patient-specific functional targeting of the GPi.

II. Background and Significance

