a. Study Design or Overview - Patients selected to undergo GPi DBS placement will be eligible for enrollment in the study. In addition to standard-of-care tests, subjects will undergo an MRI consisting of the proposed novel imaging protocol prior to placement of DBS. The patient will subsequently undergo standard-of-care therapy for DBS placement. Once the stimulator has been programmed post-operatively, the stimulation parameters and corresponding clinical changes will be collected and used to model the volume of activated tissue. The patient will additionally undergo a follow-up MRI used to localize the electrode within the brain to further localize the volume of activated tissue.

b. Study Subjects - Patients presenting to Mayo Clinic Neurosurgery identified to undergo deep brain stimulator placement in the GPi will be identified as potential subjects. Exclusion criteria for the proposed study would be any patient with contraindication to 3 Tesla MRI.

c. Sample Size - Due to the lack of any adequate preliminary studies, a sample size is estimated without statistical basis. A sample size of ten was chosen based on expected recruitment possibilities and sufficient size to prove feasibility and estimate power size for subsequent studies.

d. Data Collection -

Pre-Operative: Relevant clinical information will be collected including demographic data (age, gender), duration of Parkinson's disease, medication history, and a Unified Parkinson Disease Rating Scale (UPDRS) score. Pre-operative MRI will consist of a robust, multi-shell diffusion sequence at high resolution (1.5 x 1.5 x 1.5 mm voxel; b =1000, 2000; 64-directions, AP and PA phase encoding). Additional routine structural imaging consisting of T1-weighted MP-RAGE and FGATIR will also be obtained for purposes of identifying targets for segmentation.

Post-Operative: Clinical data will consist of post-treatment UPDRS score, complications related to DBS placement (e.g. infection, hemorrhage), and the stimulation parameters (voltage and contacts used) from the DBS programming to go with the tremor scoring. Stimulation parameters will also be recorded for any DBS programming that resulted in adverse effects, as well as the effect elicited. The patient will undergo an additional post-operative MRI using a T1 MP-RAGE sequence for purposes of localizing the final lead position.

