e. Data Handling - All data will be collected in an anonymized fashion with unique coded identifiers for each subject. The identifier linking to the patient will be stored in a separate password-protected spreadsheet for purposes of collecting data at each of the timepoints in the study.

Clinical data will be tabulated within an Excel spreadsheet that is also password protected and recorded by anonymized ID. The imaging data will be downloaded from the MRI scanner on an encrypted drive and transferred to a password-protected and encrypted Mayo Clinic computer only accessible to the PI. Imaging data will be collected and stored without patient identifiers, only by unique study ID. Processing of the imaging data will be performed and saved on the computer.

f. Data Analysis - MP-RAGE structural scans will be coregistered to the diffusion data and automatically segmented into regions of interest using FreeSurfer software. Regions of interest will consist of: (1) prefrontal cortex, (2) supplementary motor area, (3) premotor cortex, (4) primary motor cortex, (5) putamen, (6) caudate, (7) thalamus, (8) globus pallidus externus, (9) pedunculopontine nucleus, and (10) subthalamic nucleus.

The diffusion data will be used to determine voxel-wise diffusion parameters using a Markov Chain Monte Carlo sampling in the FMRIB Software Library (FSL) “bedpostx” function. A multi-fiber approach (2 fiber orientations) using a multi-shell model will be used. To perform GPi segmentation based on structural connectivity, we will utilize a probabilistic tractography method by way of FSL’s “probtrackx” to calculate probability of connection of each GPi voxel to the predefined volumes of interest (above). Each GPi voxel will then be assigned to the one target with the greatest number of propagated paths by using FSL’s “find_the_biggest” function.

Using the MP-RAGE and FGATIR MRI data, the target point for DBS placement will be determined using current standard of care. The amount of overlap between this target and each of the GPi functional segments will be calculated.

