The postoperative MRI scan will be coregistered to the pre-operative scans. The final location of the DBS lead will be calculated using LEAD-DBS software. Based on the stimulation parameters, the volume of activated tissue will be calculated with respect to lead localization. The amount of overlap between the volume of activated tissue (VAT) and each GPi segment will be calculated. Linear regression analysis will be performed to determine the degree of improvement in tremor score and degree of overlap between the VAT and each GPi segment. We hypothesize greater overlap between the VAT and GPi segment maximally connected to the primary motor cortex will result in a greater improvement in clinical improvement.

g. Feasibility and Time Frame – The expected timecourse for the study is one year. We would anticipate ~25 patients per year to be potential subjects based on historical figures of number of GPi DBS placements done at Mayo Clinic Florida. The timetable for each individual subject should be <6 weeks. Processing time for each subject is expected to be ~1 week. Since the study is incorporated into current standard-of-care clinical workflow (e.g.

imaging prior to surgery and followup imaging at time of return clinical visit), we anticipate high subject retention.

h. Strengths – The strength of the study lies in the robust diffusion sequence obtained by way of the recently released “multiband” diffusion MRI sequence. This allows a substantial improvement in resolution and data quality compared to traditional methods. Additionally, the prospective nature allows us to collect not only optimal therapeutic DBS stimulation parameters, but also those which produce unintended side effects. By capturing this additional data, it will help us to shed light on the cause of these unintended effects and potentially improve the pre-operative functional targeting. Lastly, the significant experience of the investigators in functional neuroimaging and deep brain stimulation is a significant benefit in preparing the study design and interpreting the data.

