** All programming settings will be collected throughout the duration of the study, including intra-operative and peri-operative programming/testing

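### The plan describes the inputs to the volume of activated tissue in three different ways and does not require the overlap measures to be fixed before they are linked to the clinical scores

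*Combined protocol and SAP*

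**What the plan says.** Three places in the combined protocol and SAP describe how the VAT is obtained.

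- **Section IV.a, Study Design or Overview:** "the stimulation parameters and corresponding clinical changes will be collected and used to model the volume of activated tissue".
- **Section IV.f, Data Analysis:** "Based on the stimulation parameters, the volume of activated tissue will be calculated with respect to lead localization".
- **Section I, Aim 3a:** "Based on the stimulation parameters used to achieve a satisfactory treatment response, a model of the volume of activated tissue will be generated".

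IV.f then sets the test, to be run for every functional segment: "Linear regression analysis will be performed to determine the degree of improvement in tremor score and degree of overlap between the VAT and each GPi". The stated hypothesis is that more overlap with the segment most connected to primary motor cortex goes with more improvement.

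On the pool of settings, the second footnote to the study activity table says: "All programming settings will be collected throughout the duration of the study, including intra-operative and peri-operative programming/testing".

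On handling, section IV.e has the images "transferred to a password-protected and encrypted Mayo Clinic computer only accessible to the PI", and adds: "Processing of the imaging data will be performed and saved on the computer". Clinical data go into a separate password-protected spreadsheet under the coded ID. No section gives an order of work, says whether whoever processes the images may see the scores, or says when the two sets of data are joined.

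**The concern.** The regression in IV.f is informative only if the overlap measure is obtained independently of the clinical improvement it is meant to explain. Under the literal wording of IV.a, clinical change is an input to the VAT. Under Aim 3a, response decides which setting the VAT is computed from. Under IV.f, neither applies. These are three different predictors, and the plan does not say which one is meant.

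Even on the IV.f reading, four steps leave room for judgement: outlining the GPi, coregistering the post-operative scan, localising the lead, and choosing among the recorded settings. If scores are known when these choices are made, reasonable decisions can drift towards the hypothesis.

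What is at stake is mainly the estimate, not a significance claim. Section IV.c wants the ten patients to inform the power of later studies, and Aim 3b makes the data the basis for further funding. This regression is the plan's only test of overlap against clinical improvement.

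**Working it through.** **Step 1: the text, side by side**

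| Place | What determines the VAT | Role of clinical response |
|---|---|---|
| IV.a | Stimulation parameters and clinical changes | Input to the model, read literally |
| IV.f | Stimulation parameters and lead location | None |
| Aim 3a | Settings that gave a satisfactory response | Selects the setting |

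These cannot all be the rule.

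**Step 2: where discretion remains**

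- Automated or rule-based (IV.f): FreeSurfer regions, FSL tractography, and assignment of each voxel to the target receiving the most paths, all from pre-operative scans.
- Open: the GPi is not among the ten listed regions and no method of outlining it is given. Post-operative coregistration and checks on lead localisation involve judgement. All settings are collected, but no rule says which one enters the regression.

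**Step 3: illustrative size**

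The plan has no figure to reproduce: IV.c says the sample size has no statistical basis. The only document input is n = 10. Assumed here: a two-sided 5% test, and two defensible overlap values per patient with correlation ρ of 0.9, 0.8 or 0.7.

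Critical correlation at n = 10: t(0.975, 8 df) = 2.306, so |r| = 2.306 / √(2.306² + 8) = 0.632.

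Suppose there is no true association, and each patient with above-average improvement gets the higher overlap value while each of the others gets the lower. In standard-deviation units:

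- expected shift per patient = √((1 − ρ)/π);
- induced large-sample correlation = shift × √(2/π) = √(2(1 − ρ))/π.

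For ρ = 0.9: √0.2/π = 0.14. For 0.8: √0.4/π = 0.20. For 0.7: √0.6/π = 0.25.

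Simulation at n = 10 (200,000 runs, sign taken from the sample-centred outcome) gives slightly higher values:

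| ρ | Mean r, all patients | Two-sided error, all | Mean r, half | Two-sided error, half |
|---|---|---|---|---|
| 0.9 | 0.15 | 6.9% | 0.08 | 5.4% |
| 0.8 | 0.21 | 8.9% | 0.11 | 6.0% |
| 0.7 | 0.26 | 11.0% | 0.13 | 6.4% |

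In the half columns each patient has a 50% chance of being affected. With no selection the error is 5% and mean r is zero.

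**Step 4: a different mechanism**

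Suppose instead that one variant is chosen for the whole cohort, the one with the largest |r|. The two-sided error is then 7.4% to 9.3% for two variants and 8.6% to 12.9% for three, as the correlation between variants falls from 0.9 to 0.5 (100,000 runs).

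**The case against.** The strongest reply is that IV.a is a compressed summary: both items are collected, and the parameters are used for the model. IV.f is the operative text and has no clinical input. In Aim 3a, response only identifies the setting. This stands. A reader might infer from IV.a that the plan feeds the outcome into the VAT model, but one overview sentence, contradicted by the analysis section, does not support that. It supports only the need to reconcile the wording.

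A reader might also infer from "password-protected and encrypted Mayo Clinic computer only accessible to the PI" that the images are processed by someone who already knows the scores. The documents do not say so. The phrase is a data-security measure, clinical data are held separately, and no section says who sees the scores or when. The gap is silence, not evidence of unblinded processing.

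Much of the segmentation is automated and uses pre-operative scans, which narrows the exposure to the open items in step 2. The simulated selection is also a constructed worst case: it requires two usable versions in every patient and the favourable one every time.

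Finally, this is a ten-patient feasibility study, and section IV.i accepts that results may not reach significance. That weakens any argument from false positives. It does not answer the point about the estimate, because a biased r carries forward whether or not it is significant.

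**Conclusion.** The point holds in a limited form. The three descriptions of the VAT inputs conflict. No section fixes segmentation, lead position, setting choice and VAT before scores are linked, so the outcome could inform the predictor. The documents do not show that it will.

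Under the step 3 assumptions, spurious mean correlation ranges from about 0.08 to 0.13 (half the patients affected) to about 0.15 to 0.26 (all affected). The two-sided error ranges from about 5.4% to 6.4% up to about 7% to 11%, against 5%. The documents give no alpha, sidedness, VAT radius or correlation between versions, so these figures show possible scale and do not estimate bias in this trial.

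The main consequence is an overlap-outcome estimate that may be too favourable when it is used to plan the next study. The change is worth making because it costs little; it does not call the feasibility aims into question.

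**What to change.** 1. **Reconcile Aim 3a, IV.a and IV.f.** State that only stimulation parameters and lead position enter the VAT model, and that clinical change is collected separately as the outcome.
2. **State in advance which recorded setting defines the VAT in the regression.** This is an analysis rule only and has no bearing on programming. It removes the analyst's choice; it does not remove the fact that settings are themselves programmed in response to symptoms, which should be noted as a limitation.
3. **Add an order of work to IV.f.** Finalise the GPi outline and segmentation from the pre-operative scan. Then compute lead position, VAT and overlaps by coded ID, without sight of the tremor or UPDRS scores. Save a dated overlap table, and only then merge the clinical spreadsheet. The stimulation settings needed for the VAT should reach the image processor without the scores.

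The cost is a few sentences and a fixed sequence. IV.e already keeps imaging and clinical data apart under coded IDs, so no extra patients, scans or second reader are needed.

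### The regression of tremor improvement on VAT overlap has no baseline term; with ten patients, chance severity differences can distort a given estimate, so adjusted and unadjusted slopes should be reported together

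*Combined protocol and SAP*

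**What the plan says.** Section IV.f (Data Analysis) first derives the predictor: "The amount of overlap between the volume of activated tissue (VAT) and each GPi segment will be calculated". It then gives the model in one sentence: "Linear regression analysis will be performed to determine the degree of improvement in tremor score and degree of overlap between the VAT" and each segment. The stated hypothesis is that more overlap with the primary-motor segment goes with more clinical improvement. No covariate is named, and the text does not say whether improvement is an absolute or a percentage change.

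Section IV.d (Data Collection) lists, before surgery, "medication history, and a Unified Parkinson Disease Rating Scale (UPDRS) score". After surgery it says: "Clinical data will consist of post-treatment UPDRS score". Tremor appears only in the post-operative paragraph, where stimulation parameters are recorded "from the DBS programming to go with the tremor scoring". The tremor score is not defined as an instrument or as part of the UPDRS, and no pre-operative tremor value is listed.

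On size, section IV.c says "A sample size of ten was chosen based on expected recruitment possibilities", after stating that "a sample size is estimated without statistical basis".

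**The concern.** An absolute improvement is a function of the pre-operative score: patients who start worse have more room to improve. Overlap is not assigned. It follows from lead position and stimulation settings, and Aim 3a builds the activated volume from the settings that gave an acceptable response. Nothing in the design balances severity across values of overlap, and ten patients are too few for balance to be expected by chance. A regression on overlap alone therefore cannot show how much of its slope reflects targeting and how much reflects who was sicker at the start.

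Section IV.c wants the ten patients to inform the power of later studies. If this slope were used for that purpose, a value inflated by severity would make the next study too small.

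**Working it through.** **The plan's own figure.** The only one is n = 10, declared to have no statistical basis. No alpha, effect size, SD or pre/post correlation is given, so there is nothing to reproduce.

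**Assumed inputs.** Unit SDs; improvement I = B − Y (baseline minus post-operative score); ρ = pre/post correlation apart from any overlap effect, 0.3 to 0.8; c = true correlation of baseline with overlap X; two-sided 0.05. Simulated results use 100,000 trials per setting unless noted.

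**Step 1: how baseline enters.** If Y = ρB − βX + e, then I = (1 − ρ)B + βX − e. Regressing I on X alone estimates β + (1 − ρ)·b, where b is the slope of B on X in the sample. Adding B removes the second term.

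**Step 2: average over repeated samples, c = 0.** The mean of b is 0. Simulated mean error of the unadjusted slope is 0.00 at every ρ, and type I error is 0.050 to 0.051. There is no bias.

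**Step 3: a single sample, c = 0.** The sample correlation r of baseline with overlap has SD 1/√9 = 0.33. For |r| > 0.3, t = 0.3·√8/√(1 − 0.09) = 0.89 on 8 df, a two-sided probability of about 0.40, so about 20% in each tail. Given r > +0.3, the mean shift of the unadjusted slope is in the last column below. With ρ = 0.5 and a true slope of 0.50, the unadjusted slope then averages 0.75 and the adjusted slope 0.50. In the opposite tail the unadjusted slope averages about 0.25.

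**Step 4: precision, c = 0.** Var(unadjusted) = 2(1 − ρ)/(n − 3); Var(adjusted) = (1 − ρ²)/(n − 4). The ratio adjusted/unadjusted is (1 + ρ)/2 × 7/6, which equals 1 at ρ = 12/7 − 1 = 0.71.

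| ρ | SD unadjusted | SD adjusted | Variance ratio | Mean shift if r > +0.3 |
|---|---|---|---|---|
| 0.3 | 0.45 | 0.39 | 0.76 | +0.35 |
| 0.5 | 0.38 | 0.35 | 0.88 | +0.25 |
| 0.7 | 0.29 | 0.29 | 0.99 | +0.15 |
| 0.8 | 0.24 | 0.25 | 1.05 | +0.10 |

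At ρ = 0.5 and a true slope of 0.50, power moves only from 26% to 29%.

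**Step 5: severity truly related to overlap.** Two data models with the same correlations give opposite answers.

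- *Post-operative score depends on the observed baseline.* Unadjusted bias is (1 − ρ)c. With c = 0.3 this is 0.7 × 0.3 = 0.21, then 0.15, 0.09 and 0.06 for ρ = 0.5, 0.7 and 0.8; type I error runs from 0.077 down to 0.059. Adjusted bias is about 0. With c = 0.33 and ρ = 0.5 the unadjusted bias is 0.5 × 0.33 = 0.165, about 0.17.
- *Both scores are noisy readings of one stable severity.* Take ρ = 0.5, c = 0.33 and no true effect. Overlap then correlates 0.33 with both scores, so its covariance with I is 0 and the unadjusted slope is 0.00. The adjusted slope, in the direction of improvement, is −(0.33 − 0.5 × 0.33)/(1 − 0.33²) = −0.165/0.891 = −0.185. Simulation gave −0.18 to −0.19.

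When c = 0 the two models imply the same joint distribution of the scores, so the benefit in step 3 holds under both.

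**The case against.** The strongest objection is that adjustment is no cure here. In observational data the choice between a change score and baseline adjustment is contested, and step 5 shows that adjusting can create a bias about as large as the one it removes. This stands. It is the reason to report both slopes rather than replace one with the other.

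The precision gain is small and disappears at a pre/post correlation of about 0.7. This also stands; precision alone would not justify the change.

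This is a feasibility study, and section IV.i already says that significance may not be reached. That lowers the stakes but does not dispose of the point, which concerns the estimate and not its p-value.

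A reader might also infer more than the documents support:

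- *The baseline needed is already in hand.* What is listed is the UPDRS, while the regression outcome is a tremor score with no listed pre-operative value. Whether new data are needed depends on how that score is defined.
- *The plan analyses raw differences.* It does not define improvement. The figures above assume an absolute difference and would not carry over directly to a percentage change.
- *This slope is the main evidence for Aim 3.* Aim 3a concerns the overlap of the activated volume with the functional and atlas targets, and does not mention a regression on improvement.

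**Conclusion.** The point holds in a limited form. The regression has no baseline term, its predictor is not randomised, and with ten patients a baseline-overlap correlation beyond ±0.3 arises by chance in about 40% of samples. In the upper half of those (about 20% of all samples) the unadjusted slope is too high by about 0.25 on average at a pre/post correlation of 0.5, and by 0.10 to 0.35 over correlations of 0.8 down to 0.3. The lower half errs by a similar amount in the other direction.

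It would be wrong to conclude that chance imbalance biases the slope: the two tails cancel and type I error stays at 5%. It would also be wrong to treat the adjusted slope as the correct one whatever the truth. If severity is really related to overlap, which the documents neither show nor exclude, the data-generating process decides which slope is biased.

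All SDs and correlations are assumptions. The consequence is modest for a pilot, but the remedy is cheap.

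**What to change.** In IV.f:

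1. Name the tremor score, say how improvement is computed, and use the same instrument's pre-operative value as baseline (for example the UPDRS tremor items, if they are available at both visits). List that value in IV.d.
2. For each GPi segment, with the primary-motor segment identified as the hypothesised one, fit the post-operative score on the pre-operative score plus VAT overlap. Report the overlap slope with its 95% CI.
3. Report the unadjusted improvement slope next to it, stated in the same direction. Say in advance that a material difference will be read as a sign that severity and targeting cannot be separated in these data.

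The cost is a few sentences and one residual degree of freedom (7 instead of 8). If the pre/post correlation exceeds about 0.7 there is a slight loss of precision, with variance about 5% higher at 0.8. No new data are needed if the tremor score comes from a UPDRS already recorded at item level at both visits; otherwise a pre-operative tremor score has to be added. Adjustment for baseline will not remove other confounders of overlap.

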Parkinson's disease (PD) is a common, debilitating neurologic disease. Over one million people suffer from PD in the United States alone. Deep brain stimulation (DBS) has been shown to be an effective treatment option. One of the most frequent targets for DBS in PD is the globus pallidus internus (GPi).

One limitation of surgical (e.g., DBS) treatment for PD is the inability to identify functional brain targets pre-operatively. Current methods rely on atlas-based approaches or coordinate-based stereotaxy where a specific coordinate, based on larger landmarks, is presumed to be the approximate location of the targeted functional region in all patients. These targeting methods rely on standardized coordinates that do not account for known inter-individual variations in functional anatomy. In fact, it has been previously reported that 46% of patients

with poor response to DBS therapy have malpositioned DBS leads.² There is also disagreement in the choice of ideal atlas-based coordinates. Perhaps most concerning regarding all methods of structural localization is the assumption that brain function is predictable by brain structure. The validity of such assumption is questionable as it has been shown that brain functional localization may vary significantly from predictions based solely on structure. It is now well-known that pathologic changes in the brain can result in variations in the relationship of structure and function due to neural plasticity.

The idea of brain connectomics is a rapidly developing field of neuroscience. The ability to examine *in vivo* human brain functional connectivity has revealed new insight into many neurologic and neuropsychological conditions. To date, the clinical impact of connectomics has been limited. The origin of the current proposal was the belief that this emerging technology could be applied to a very specific problem in clinical medicine not well-addressed by current techniques. As such, this project would ideally serve as a model and further proof that such science can be currently translated into clinical medicine.

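### The only analysis tied to benefit uses the patient's own map, so a positive overlap slope cannot by itself support the patient-specific claim of Aim 3

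*Combined protocol and SAP*

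**What the plan says.** Section I, Aim 3 states the purpose: "To compile preliminary evidence for the role of a patient-specific, functional-based targeting protocol to replace potentially inaccurate atlas-based methods". Section II gives the reason for distrusting atlas methods: "These targeting methods rely on standardized coordinates that do not account for known inter-individual variations in functional anatomy".

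Section IV.f builds the map separately for each patient from that patient's tractography: "Each GPi voxel will then be assigned to the one target with the greatest number of propagated paths". No group-average or normative map is described. The same section then has one analysis that involves clinical outcome, a linear regression described as concerning "degree of improvement in tremor score and degree of overlap between the VAT and each GPi segment". The expected result is "We hypothesize greater overlap between the VAT and GPi segment maximally connected to the primary motor cortex will result in a greater improvement".

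Two other analyses bear on the atlas. Aim 2 describes how far the traditional target point overlaps each functional segment and how this varies between patients. Aim 3a says: "The degree of overlap between this volume of tissue will be assessed on both the pre-operative functional target and the original atlas-based target". Neither is related to improvement, and section IV.f gives no VAT-versus-atlas calculation.

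**The concern.** The patient-specific claim is comparative: this patient's map must tell us something about benefit that a map or coordinate common to all patients does not. The planned regression has no such comparison. If the motor segment lies in roughly the same part of the GPi in most patients, a lead near that common site will overlap well with the patient's own segment, whether or not the individual map adds anything. A positive slope is then expected both when the individual map matters and when only the usual motor location matters.

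Aim 3b makes these data the basis for further funding, and section IV.c wants them to inform the size of later studies. If the slope is taken as support for individual mapping, the next study could be justified by, and sized on, a quantity that does not measure the advantage claimed.

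**Working it through.** **Figures in the plan.** The sample size is ten: "A sample size of ten was chosen based on expected recruitment possibilities". Section IV.c adds that "a sample size is estimated without statistical basis". With no alpha, power, effect size or SD given, there is no calculation to reproduce. The check is therefore of what the planned slope can distinguish.

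**Geometric model, by simulation (all SDs assumed, in mm per axis, three dimensions).**
- Individual motor site: c ~ N(0, s²), with s = 0.5 or 1.
- Lead position: l ~ N(0, L²), with L = 0.5 to 2.
- Estimated map centre: m = c + error, with error SD 0.5.
- Improvement: y = -distance(l, site) + N(0, 1). The site is c if benefit is individual, or 0 if only the shared centre matters.
- Own-map predictor: -distance(l, m). Proximity stands in for overlap.
- Test: t = r√8/√(1 - r²) against 2.306 (two-sided 0.05, 8 degrees of freedom). This requires r above 2.306/√(8 + 2.306²) = 0.63.

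Share of pilots in which the own-map slope is positive, and positive and significant:

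| Lead SD L | Shared site only (s = 0.5 to 1) | Individual site (s = 1) |
|---|---|---|
| 0.5 | 55-61%; 3-5% | 94%; 32% |
| 1.0 | 76-86%; 10-18% | 98%; 50% |
| 1.5 | 91-97%; 26-44% | 99%; 70% |
| 2.0 | 97-99%; 48-69% | nearly 100%; 85% |

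In the shared-site column, the higher figure of each pair belongs to s = 0.5, where patients differ least.

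**Second model, using correlations instead of geometry.** Let r be the correlation of the true driver with improvement, and ρ the correlation between own-map and shared-map overlap (both assumed). If only the shared map matters, the own map still correlates with improvement at r × ρ. For r = 0.6 and ρ = 0.5, 0.7, 0.9 this is 0.30, 0.42, 0.54. With n = 10 the own-map slope is then positive in 81%, 90% and 96% of runs and significant in 13%, 23% and 39%. For r = 0.8 the figures are 89%, 97%, 99% and 21%, 42%, 72%. If the own map is the true driver, the slope is significant in 49% (r = 0.6) or 87% (r = 0.8).

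**What a comparison could show at n = 10.** In the geometric model with L = 1.5 and map error 0.5, the own map correlates better with improvement than the average of the other nine in 83% of pilots if benefit is individual and about 18% if it is shared (s = 1), or 56% against 24% (s = 0.5). These are comparisons of sign only. A bootstrap 95% interval for the difference excluded zero in favour of the own map in only about 14% (s = 1) or 4% (s = 0.5) of truly individual pilots. In the correlation model, the own-map slope adjusted for the shared map has 12-35% power at r = 0.6 and 29-73% at r = 0.8.

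**The case against.** Four points can be made for the plan.

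- It does contain atlas comparators, in Aims 2 and 3a. True, and a reader who inferred that the plan has no comparator at all would be wrong. But both are comparisons of overlap only. Variation in overlap could also arise from tractography error, so it does not show that the differences matter clinically.
- The protocol sets itself against atlas targeting and never claims to beat a group-average connectivity map. This stands in part. The atlas target of Aim 3a is the comparator closest to the stated aim and should be included. It is, however, a point rather than an average motor map, so it does not fully answer whether an individual scan is needed.
- This is a feasibility pilot. Section IV.i expects that significance may not be reached, Aim 3c leaves efficacy to a later trial, and section V says the data will not guide care. No decision rule is stated. This stands: the risk is over-interpretation and a weakly grounded follow-up, not a wrong confirmatory conclusion.
- The slope is not uninformative. With lead SD 0.5 to 1.0 mm and individual SD 1 mm, it is significant in 32-50% of pilots if benefit is individual and 3-10% if it is shared. This stands too, and the size of the problem is conditional on lead scatter.

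A reader might also infer that only an own map that beats the group map would count as evidence. That goes too far. Averaging nine maps removes noise that a single map keeps. At L = 1.5 with map error 1 mm, the own map wins in only 34% (s = 0.5) or 64% (s = 1) of pilots in which benefit is truly individual; at 1.5 mm error, 26% or 50%. The voxel in section IV.d is 1.5 mm, so errors of this order cannot be dismissed.

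**Conclusion.** The gap is real. As section IV.f is written, a positive own-map slope cannot establish an advantage of patient-specific targeting, because no shared or atlas predictor is related to improvement.

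How misleading the slope would be cannot be fixed from the documents, which give no lead scatter, anatomical variation or map error. Over the assumed range it is positive in anything from about 55% to 99% of pilots when only the shared site matters, and significant in about 3% to 69%. It is tempting to say that a positive result is nearly as likely when individual mapping adds nothing. That fits only the sign of the slope, and only with wider lead scatter; it is not true of significance across the range.

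The point merits a change to the analysis text. It does not undermine the feasibility aim.

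**What to change.** In section IV.f, for each VAT, also compute:

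1. overlap with, or distance to, the atlas-based target already named in Aim 3a;
2. overlap with the primary motor segment averaged over the other nine patients and warped to this patient's anatomy (leave-one-out).

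Relate each to improvement alongside the own-map overlap, and report the own-minus-comparator difference with an interval, labelled exploratory. Add two sentences on interpretation: a positive own-map slope alone does not establish a patient-specific advantage; and failure of the own map to beat the group map does not rule one out, because a single map is noisier than an average of nine.

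The cost is some registration and analysis work on scans already planned, with no new patients or data. The interval will be wide at n = 10: even a single correlation of 0.6 has a 95% interval of tanh(0.693 ± 1.96/√7), about -0.05 to 0.89.
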